7.1.3 Secondary Endpoints

- 1. Safety: the safety of LAU-7b therapy will be assessed through the monitoring of treatment emergent adverse events and serious adverse events, vital signs including oxygen saturation and body temperature, symptom-directed physical examinations and safety laboratory tests. It is important to note that most of these assessments are also SOC for hospitalized patients with COVID-19 disease and changes from baseline can depict improvement or worsening of the condition.
- 2. Efficacy: Rate of all-causes death, depicted by a change from baseline in the ordinal scale position to category 7 by Days 29 and 60, compared between the active and control (placebo) arms of the study.
- 3. Efficacy: Rate of COVID-19 disease-related transfer to mechanical ventilation, depicted by a change from baseline in the ordinal scale position to category 6, compared between the active and control (placebo) arms of the study.
- 4. Efficacy: Proportion of patients alive and free of respiratory failure by Day 29 (ordinal scale scores 1-4, inclusively), compared between the active and control (placebo) arms of the study.
- 5. Efficacy: Proportion of patients re-hospitalized after discharge (any stay in the hospital of minimum overnight duration, all causes) up to Day 60, compared between the active and control (placebo) arms of the study.
- 6. Efficacy: Rate of COVID-19 disease-related aggravation, depicted by a change from baseline in the ordinal scale position of at least one category, compared between the active and control (placebo) arms of the study.
- 7. Efficacy: Rate of COVID-19 disease-related transfer to ICU, compared between the active and control (placebo) arms of the study.
- 8. Efficacy: Patient status on the 7-point ordinal scale on Days 14 and 29; compared between the active and control (placebo) arms of the study.
- 9. Efficacy: Mean change from baseline of the ordinal scale patient status as a function of assessment time, compared between the active and control (placebo) arms of the study.
- 10. Efficacy: Time to an improvement of one category on the ordinal scale patient status, compared between the active and control (placebo) arms of the study.
- 11. Efficacy: Time to recovery, defined here as a move from baseline to categories 2 or 1 on the ordinal scale patient status (first occurrence if more than one), compared between the active and control (placebo) arms of the study.
- 12. Efficacy: Time to mechanical ventilation, defined here as a move from baseline to category 6 on the ordinal scale patient status, compared between the active and control (placebo) arms of the study.
- 13. Efficacy: Time to death, defined here as a move from baseline to category 7 on the ordinal scale patient status, censored to Day 60 if it happens later than Day 60, compared between the active and control (placebo) arms of the study.
- 14. Efficacy: Duration of hospitalization (days) within the study period Days 1-60, compared between the active and control (placebo) arms of the study.
- 15. Quality-of-Life: The change from baseline to Days 14, 29, 45 and 60 in the score obtained on the EQ-5D-5L survey, a well-documented scoring system that has been widely used and validated as a QoL assessment tool, compared between the active and control (placebo) arms of the study, in patients reaching Days 14, 29, 45 and 60 and able to fill the questionnaire.

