In subgroups 3 and/or 4 (and the combined 3+4 subgroup as well) LAU-7b plus standard of care showed a 100% reduction in the risk of all-causes death and the risk of progressing to invasive mechanical ventilation by Day 60, when compared to placebo plus standard of care, as well as an improvement in the proportion of patients alive and without respiratory failure at Day 29, a faster recovery and shorter hospitalization.

More specifically, none of the 76 moderately to severely ill COVID-19 patients treated with LAU-7b died or progressed to mechanical ventilation, while 4 patients died (4/72, 5.6%, p=0.053) and 5 progressed to mechanical ventilation (5/72, 6.9%, p=0.025) in the placebo arm. For some endpoints, the positive trend is more evident in subgroup 3 while for others, it is subgroup 4 which shows the higher benefit. Combining them increases the sample size and approaches statistical significance. This is indicative that the combined 3+4 population should be studied further to confirm the results above. This positive signal, in particular the total prevention of the need for mechanical ventilation or mortality in subgroups 3 and 4, was recognized by clinicians as being clinically relevant and worthy of clinical confirmation for this particularly underserved hospitalized population. Avoiding at all costs the progression toward respiratory failure and the need for ICU and invasive mechanical ventilation is a high priority.

The subgroup analysis of critically ill COVID-19 patients didn't show an improvement in the LAU-7b arm over placebo, suggesting that patients already in respiratory failure at baseline may be too severely affected by the disease to benefit from LAU-7b treatment.

Summary:

In conclusion, patients that were not in respiratory failure at baseline (Moderate-to-Severe COVID, Health Status 3 and 4) responded positively to treatment with LAU-7b, supporting further evaluation in this patient subset. Safety was excellent in the overall Safety population and particularly in the Moderate-to-Severe COVID patients.

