7.2 Study Overview

7.2.1 Description

RESOLUTION is a multicentre, randomized, double-blind (patients, Investigators and blinded study staff), placebo-controlled Phase II study of LAU-7b for the treatment of COVID-19 disease in patients at a higher risk than the general COVID-19 disease population to develop complications while hospitalized.

To be eligible for the study, patients must be symptomatic of COVID-19, confirmed by PCR (or alternates but excluding rapid antigen tests)) to have a SARS-CoV-2 infection, be aged 18 years and above, and meet all other study inclusion and none of the exclusion criteria at screening. There is no time limit between the onset of symptoms or the confirmation of SARS-CoV-2 infection and screening.

Eligible patients will be randomized 1:1, at each clinical site, to either LAU-7b (active) group or placebo (control) group. After randomization, patients will enter the treatment phase of the study. There will be no active control treatment but patients will undergo the COVID-19 disease SOC at their institution.

Since the study randomizes only confirmed cases of SARS-CoV-2 infection, the screen failure rate is very low. It is estimated that based on sample size calculation using the effect size observed in the pilot portion of the study for the revised Primary Efficacy Endpoint in the subset of patients with Health Status score 3 or 4 at baseline, up to a total of approximately 264 patients with a Health Status score 3 or 4 at baseline will be recruited in the expansion. Patients will be enrolled at approximately 25-30 centers in the United States of America and in Canada. The study treatment (LAU-7b or matching placebo) will be administered once a day in the fed state (with the main meal of the day if possible) for up to 14 days on treatment.

Patients will be evaluated at pre-specified times during and after the study treatment period, for efficacy, safety, as well as for Quality of Life.

This design is appropriate for this phase of development (confirmatory Phase 3 portion) and will ensure that the highest quality of data is collected with minimal bias and the patient's safety and wellbeing are preserved. A Data and Safety Monitoring Board (DSMB) is monitoring this study.

The overall study structure for Health Status 3+4 patients in the Phase 2 pilot and the Phase 3 extension is presented below in Figure 2.

[figure not shown]

Figure 2: Overall structure of the study

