Using the proportion of patients requiring mechanical ventilation AND/OR deceased by Day 60 in the pilot portion of the study, an effect size of 7% change (i.e. 7% in the control group vs. 0% in the investigational group), comparing the active arm versus the control (placebo) arm, and a minimum of 90% statistical power of detecting a difference of 7% using a two-tailed Fisher Exact test, with a nominal alpha of 0.05, a total sample size of 264 patients (132 per arm) with a Heath Status score of 3 or 4 at baseline is required for the Phase 3 confirmatory portion of this study.

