12.7.2 Analysis of Secondary Efficacy Endpoints

Pre-defined Clinical Parameters:

- The ordinal scale will be used to estimate a proportional odds model. The primary hypothesis test will be based on a test of whether the common odds ratio for treatment is equal to one. The model fit using a goodness-of-fit likelihood ratio test will be evaluated. The distribution of severity results will be summarized by treatment arm as percentages. The validity of the proportionality assumption will be evaluated and tested. Participants without final outcome data will be excluded from the analysis. Sensitivity analyses will evaluate the impact of making different assumptions about missing observations. These sensitivity analyses will be fully defined in the SAP.
- Count data variables: The number of days of hospitalization, the number of days in ICU, the number of days under mechanical ventilation...etc., will be tabulated by treatment and compared with an appropriate count data model, e.g., ANOVA model (if assumptions of normality and homogeneity of variance appear acceptable), Poisson regression, negative binomial regression, zero-inflated regression, etc., depending on their distribution.
- Time to event data variables: The time to mechanical ventilation, time to recovery, time to aggravation (worsening by one category on the ordinal scale), and time to death will be tabulated by treatment and compared using a Cox proportional hazards model. If the proportional hazards assumption is violated, a stratified analysis will be conducted using stratified Cox regression. Additionally, Kaplan-Meier methods will be used to produce graphical presentations of the survival (aggravation-free survival, survival) by treatment group and to estimate cumulative aggravation-free survival and survival rates by treatment group.
- Change in ordinal scale at specific time points will be summarized by proportions (e.g., proportion who have a 1-, 2-, 3-, or 4-point improvement or 1-, 2-, 3-, 4-point worsening).
- Mean change-from-baseline for the ordinal scale will be analyzed through time, using a mixed model repeated measure (MMRM) model.
- Body weight and BMI changes from screening will be summarized using descriptive statistics by treatment and compared between treatments using an analysis of covariance (ANCOVA) with treatment as fixed effect; and adjustment for screening Ordinal Scale Health Status, and weight or BMI at baseline as covariates.

Formal Futility Analysis (Pilot Portion):

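### No rule is given for deaths in the hospital, ICU and ventilator day counts, and a plain count would lose most of the expected mortality difference

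*Protocol*

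**What the plan says.** Protocol section 7.1.3 lists endpoint 14 as "Duration of hospitalization (days) within the study period Days 1-60", compared between arms. Section 12.7.2 groups "The number of days of hospitalization, the number of days in ICU, the number of days under mechanical ventilation" as count data, to be compared by ANOVA if its assumptions look acceptable, or by Poisson, negative binomial or zero-inflated regression. ICU days and ventilator days appear only there; they are not numbered endpoints in section 7.1.3.

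Neither section says what value a patient who dies receives. The neighbouring endpoint 13 (time to death) does carry a Day 60 censoring rule. Table 3 in section 12.4 handles death by a composite strategy, but for the primary estimand, and endpoint 14 has no death component. The SAP Addendum as supplied does not mention these variables and refers to the main SAP of 29SEP2023, which is not among the documents.

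On the pilot patients with baseline Health Status 3 or 4, section 5.4.2.1 reports for placebo that "4 patients died (4/72, 5.6%, p=0.053" (five of the 72 were ventilated), with no deaths or ventilation among 76 on LAU-7b. It also reports a shorter hospital stay on LAU-7b.

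**The concern.** If no rule exists, the default is to count the days observed. Death then ends the count: an in-hospital death on Day 5 contributes 5 days and ranks ahead of a survivor discharged on Day 8. The other easy default, leaving out patients who die, conditions on survival and removes mortality from the comparison. Neither treats death as a bad result.

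The pilot deaths were all on placebo, so the effect would differ between arms. Hospital stay was a pilot topline variable and part of the case for the expansion. A reader of the final result cannot interpret a difference in days, or its absence, without knowing how deaths were scored.

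**Working it through.** **The plan's own figure.** Section 12.1 assumes "7% in the control group vs. 0% in the investigational group", requires "a minimum of 90% statistical power of detecting a difference of 7% using a two-tailed Fisher Exact test", and states "with a nominal alpha of 0.05, a total sample size of 264 patients (132 per arm". With no active events, the two-sided Fisher test at 132 per arm rejects when control has 6 or more events. The binomial probability of that at 7% is 90.6%, so 264 is reproduced. The pilot Fisher p-values also agree, apart from rounding: 0.0536 for 4/72 v 0/76 and 0.0253 for 5/72 v 0/76. No figure is stated for the duration variables.

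**Inputs for hospital days.** q = 4/72 = 0.0556 (placebo deaths; none on LAU-7b). D is the day of in-hospital death and S the mean survivor stay, taken as equal in both arms. The documents give neither D nor S; I assume D = 3 to 30 and S = 5 to 12.

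**Formula.** From mortality alone, placebo minus LAU-7b mean stay is q × (D − S). If death counts as zero days alive and out of hospital to Day 60, LAU-7b gains q × (60 − S) days. Positive values favour LAU-7b.

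| S | D = 3 | D = 5 | D = 10 | D = 20 | D = 30 | Death = 0 days alive and out |
|---|---|---|---|---|---|---|
| 5 | −0.11 | 0.00 | +0.28 | +0.83 | +1.39 | 3.06 |
| 8 | −0.28 | −0.17 | +0.11 | +0.67 | +1.22 | 2.89 |
| 12 | −0.50 | −0.39 | −0.11 | +0.44 | +1.00 | 2.67 |

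For S = 8: 4/72 × (5 − 8) = −0.17, 4/72 × (20 − 8) = +0.67, and 4/72 × (60 − 8) = 2.89. The share retained by the plain count is (D − S)/(60 − S): 12/52 = 23% at D = 20, S = 8, and 25/55 = 45% at the most favourable corner (D = 30, S = 5). The sign turns negative only when D is less than S.

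**Simulation, 132 per arm.** Log-normal stays with median 5 or 8 days, 5.6% placebo deaths and no other treatment effect. The entries are chances of two-sided significance at 5% in favour of LAU-7b.

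| Handling of deaths | t-test | Wilcoxon |
|---|---|---|
| Plain count, median death day 3 to 6 | 1-3% | 0.3-3% |
| Plain count, median death day 12 | 4-9% | 4-8% |
| Plain count, median death day 20 | 10-23% | 8-11% |
| Deaths excluded | about 3% | 3-4% |
| Death scored worst | 50-72% | 11-12% |

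A direct Fisher test of 4/72 v 0 mortality at this size has about 75% power.

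**Ventilator days.** The pilot composite in section 12.1 is 6.9%, which is 5/72, the same as ventilation alone, so all four deaths were among the five ventilated patients. With no ventilation on LAU-7b, the mean difference is (4/72) × L + (1/72) × 14, where L is ventilator days before death and 14 days is assumed for the ventilated survivor. It is 0.36 days at L = 3, 0.97 at L = 14 and 1.75 at L = 28, against 3.53 with each death scored as 60. It is always positive.

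**ICU days.** The documents give no figures from which to set a direction.

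**The case against.** The strongest reply is that silence is not a rule. A reader might infer that the plan counts death as a short, good outcome. The documents do not say that: section 12.7.2 leaves the model open, detail is deferred to the SAP, and the main SAP was not available. That stands, and it limits the point to a missing rule and the consequence of the obvious default.

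A reader might also infer that these variables will reverse a survival benefit and favour placebo. That is not shown. Hospital days reverse only if deaths precede the mean survivor stay, and then by at most half a day over the range examined. Entry excludes patients expected to die or go to ICU within 24 hours, and the pilot deaths were all in ventilated patients, which suggests, without proving, longer stays before death. The pilot reported shorter hospitalization on LAU-7b alongside 0 v 4 deaths. Ventilator days cannot reverse when the active arm has no events.

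Mortality is also measured elsewhere: in the primary composite, the death rate at Days 29 and 60, the Day 29 endpoint on survival without respiratory failure, the ordinal status and time to death. Raw hospital days are a legitimate measure of resource use, in line with the rationale in section 6. All this stands, and the primary conclusion is untouched. It does not tell the reader what a difference in hospital days means when deaths differ between arms.

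Finally, a rank test on the better variable has low power from mortality alone. That is true and must be disclosed.

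**Conclusion.** The point holds in limited form. The supplied documents give no rule for deaths in endpoint 14 or in the ICU-day and ventilator-day counts. A plain count would put an early in-hospital death ahead of a later discharge and lose most of the expected mortality difference: −0.2 to +0.7 days against 2.9 days at an 8-day mean survivor stay, and −0.5 to +1.4 against 2.7 to 3.1 over the wider ranges. These sizes rest on pilot mortality of 4/72 v 0/76 and on assumed stay and death times. Ventilator days are diluted only; ICU days cannot be judged. The consequence is for interpreting secondary and supportive variables. The conclusion lapses if the main SAP already scores deaths adequately.

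**What to change.** First check the main SAP of 29SEP2023 for a rule. If there is none, derive days alive and out of hospital to Day 60 with death scored as 0, and ventilator-free and ICU-free days in the same way. Present them beside raw length of stay, which stays as a descriptive line with its handling of deaths stated. The SAP Addendum records that results were first released on 14MAR2024, so label these analyses post hoc and supplementary unless they were prespecified.

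The cost is a short SAP text and a derivation from data that the planned counts and the Day 60 follow-up already require. The new variables are skewed with a spike at zero, so means describe them less well, and a rank comparison has only about 11-12% power from mortality alone. The report should say so: the gain is mainly correct ordering of outcomes and a result that can be interpreted.

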7.2 Study Overview

7.2.1 Description

RESOLUTION is a multicentre, randomized, double-blind (patients, Investigators and blinded study staff), placebo-controlled Phase II study of LAU-7b for the treatment of COVID-19 disease in patients at a higher risk than the general COVID-19 disease population to develop complications while hospitalized.

To be eligible for the study, patients must be symptomatic of COVID-19, confirmed by PCR (or alternates but excluding rapid antigen tests)) to have a SARS-CoV-2 infection, be aged 18 years and above, and meet all other study inclusion and none of the exclusion criteria at screening. There is no time limit between the onset of symptoms or the confirmation of SARS-CoV-2 infection and screening.

Eligible patients will be randomized 1:1, at each clinical site, to either LAU-7b (active) group or placebo (control) group. After randomization, patients will enter the treatment phase of the study. There will be no active control treatment but patients will undergo the COVID-19 disease SOC at their institution.

Since the study randomizes only confirmed cases of SARS-CoV-2 infection, the screen failure rate is very low. It is estimated that based on sample size calculation using the effect size observed in the pilot portion of the study for the revised Primary Efficacy Endpoint in the subset of patients with Health Status score 3 or 4 at baseline, up to a total of approximately 264 patients with a Health Status score 3 or 4 at baseline will be recruited in the expansion. Patients will be enrolled at approximately 25-30 centers in the United States of America and in Canada. The study treatment (LAU-7b or matching placebo) will be administered once a day in the fed state (with the main meal of the day if possible) for up to 14 days on treatment.

Patients will be evaluated at pre-specified times during and after the study treatment period, for efficacy, safety, as well as for Quality of Life.

This design is appropriate for this phase of development (confirmatory Phase 3 portion) and will ensure that the highest quality of data is collected with minimal bias and the patient's safety and wellbeing are preserved. A Data and Safety Monitoring Board (DSMB) is monitoring this study.

The overall study structure for Health Status 3+4 patients in the Phase 2 pilot and the Phase 3 extension is presented below in Figure 2.

[figure not shown]

Figure 2: Overall structure of the study

To ensure the study is powered adequately if the effect size is smaller than initially estimated, an interim sample size re-estimation (Mehta and Pocock, 2011)⁸⁵ will occur once 42% (112) of the planned 264 patients have either completed the Day 60 primary endpoint assessment or terminated their study participation early. If the conditional power is within the promising zone, the sample size may be increased up to a maximum of 462 patients, dependent upon the results of the interim sample size re-estimation. If the conditional power is

below the promising zone, the futility criteria will be deemed met and a recommendation to stop further enrollment will be communicated to the DSMB and the Sponsor.

7.2.2 **DSMB**

Throughout the study, the DSMB monitors blinded and unblinded safety measures and demographics at regular intervals as specified in the DSMB charter, or as requested by the DSMB chair. The DSMB will receive reports of adverse events by organ class, with emphasis on SAE's, clinically significant adverse events with a high causality potential to the study treatment. Members of the DSMB are not directly involved in the conduct of the study and cannot serve as Investigators in this study.

The DSMB is composed of:

- Three physicians all involved in the care of COVID-19 disease patients, experienced in clinical research, independent of Laurent Pharmaceuticals and not involved as an Investigator on the study.
- One study biostatistician that can be unblinded with regards to patient randomization, meaning that he/she is not involved in the statistical design, analysis and reporting of the study.
- Ad-Hoc members recruited to provide specific expertise and meet the Board's mandate.

Each DSMB member signed a Conflict of Interest Statement which includes current affiliations, if any, with pharmaceutical and biotechnology companies (e.g., stockholder, consultant), and any other relationship that could be perceived as a conflict of interest related to the study and / or associated with commercial interests pertinent to study objectives.

Data will continue to be presented in a blinded manner during the open sessions of the DSMB unless noted otherwise below. At DSMB meetings data and discussion are confidential. Participant identities will not be known to the DSMB members.

Mandate of the DSMB (defined in greater detail in the DSMB Charter):

- Review safety information emerging from the study (and any other study of fenretinide). The DSMB will have access to the randomization code, if justified.
- Meet at specific times of the study to review the safety data cumulated to date. The following specific times have been selected a priori:
 - When a minimum of a third of the enrolled patients have completed their LAU-7b (or placebo) treatment period and corresponding safety information was available. This was an unblinded safety analysis of Active versus Placebo and occurred in March 2021;
 - When a minimum of half of the enrolled patients have completed their LAU-7b (or placebo) treatment period and corresponding health status/efficacy information at Day 29 was available, a formal futility analysis (stopping rule) focusing on the proportion of patients alive and free of respiratory failure by treatment group, was performed and presented to the DSMB, seeking recommendation to pursue or stop the study, details can be found in the statistical analysis Section 12.7.2 and the analysis resulted in a DSMB recommendation to continue the study on 30Mar2021, since the criteria for futility was not met;
 - When a minimum of two thirds of the enrolled patients have completed their LAU-7b (or placebo) treatment period and corresponding safety data is available for review. This was an unblinded safety analysis of Active versus Placebo and occurred in June 2021;
 - O During the Phase 3 expansion of the study, considering the excellent safety profile observed so far, when one third and two-thirds of the required supplemental patients have completed their

- LAU-7b (or placebo) treatment period and corresponding health status/efficacy information at Day 29 is available, again an unblinded safety analysis of Active versus Placebo;
- O Review the interim sample re-estimation/futility analysis data and results. The DSMB will convey the recommendation to either continue the study with the planned sample size or increase the sample size (up to the maximum) according to the pre-defined criteria or to stop enrollment if the futility criteria has been met.
- o Independently of the above, every 6 months during the active randomization period; and
- o Anytime as needed for review of clinically significant safety information brought to the attention of the DSMB.

